6.4 STRATA AND COVARIATES

The primary efficacy analysis will be stratified by length of time after stroke (3-6 months vs. 6-12 months).

Additional covariate analyses will model the primary endpoint (a binary response of UEFM score improvement), absolute changes (in points) in the tests of motor function (UEFM, and ARAT) using hours of occupational therapy outside the trial and overall hours of therapy (occupational, physical, and home exercise) as covariates during treatment phase and over the entire 6 months of follow-up.

All covariate analysis will be performed for both ITT and PP population.

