6.0 ANALYSIS PLAN

The results of functional motor tests at end of rehabilitation (5-10 days post treatment) and at 1, 3 and 6 months after the end of rehabilitation will be compared to the results obtained at baseline to determine the functional recovery if any that has occurred. The results of patients randomized into separate groups will be compared to each other to determine the effect of rTMS.

The primary analysis population will be the intent-to-treat (ITT) population. In addition, a separate analysis will be conducted on the per protocol (PP) population.

Primary outcome measure for the trial is the Upper-extremity Fugl-Meyer score.

The beneficial effect of 1Hz NBS guided rTMS will be established if a statistically significantly greater proportion of patients receiving NBS-rTMS attain clinically important improvement in the primary outcome measure than patients receiving sham-rTMS between baseline and 6 months post-treatment.

The size of the treatment effect will be measured by the odds ratio parameter which is defined as

$$OR = \frac{P_{TRT} / (1 - P_{TRT})}{P_{REF} / (1 - P_{REF})}$$

where P_{TRT} and P_{REF} denote the proportion of subjects with clinically significant change from baseline in Fugl-Meyer score, in the treatment and reference groups respectively.

The null hypothesis is H_0 : OR = 1 and the two-sided alternative hypothesis is H_1 : $OR \neq 1$.

The proportion of responders in each treatment group will be summarized, along with the estimated odds ratio, the 95% confidence interval for OR, and the Wald Chi-square test p-value. The primary analysis will be performed on the ITT, and on the PP population as a sensitivity analysis.

Secondary outcome measures for the trial are ARAT test, , NIHSS, and EQ-5D.

Descriptive statistics will be summarized by treatment and visit. Absolute difference (in points) in improvement will be summarized for both treatment groups between baseline and 5-10 days and 1, 3 and 6 month follow-up visits and the treatment groups compared via a two-way ANOVA.

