6.1 POWER ANALYSIS AND BORROWING DATA FROM NICHE-TRIAL ACTIVE TRIAL ARM RESULTS

In a pilot study of 30 patients of whom 20 were randomized to active NBS-rTMS and 10 to sham-rTMS, 84% of the active NBS-rTMS group and 50% of the sham rTMS group attained clinically significant improvement of at least 5 points on the Fugl-Meyer score [Harvey RL 2009, Harvey RL, unpublished].

Similarly, in the completed multi-centre trial (NICHE-trial, NCT02089464) of 199 subjects using the same trial device but different sham coil design, 72% of subjects with ischemic stroke receiving active NBT-rTMS attained clinically significant improvement of at least 5 points on the Fugl-Meyer score [Harvey RL, manuscript in preparation] while the average expectation of NICHE trial site principal investigators of subjects improving was 36%.

Based on this data and sample size calculations utilizing significance level of 0.05 for p, we estimate that enrolling 60 patients need to be recruited to the present study to rule out the null hypothesis that there is no difference between active NBT-rTMS and sham-rTMS with 81% power. This assumption is based on the pilot study finding of 33% difference in responder rate between groups in favour of the NBS-rTMS group and 36% difference in the actual vs expected responder rate in patients with ischemic stroke in NICHE. However, since the active treatment arm of the present trial and the active trial arm of NICHE are treated in a completely identical manner (the same NBT device, same active rTMS protocol, the same standardized occupational therapy protocol as in NICHE, the same number of therapy sessions in the same schedule at the same trial sites, etc) this allows pooling of the data obtained in the NICHE active trial arm to the data obtained in the active trial arm in the present trial. As in NICHE there were 88 subjects with ischemic stroke receiving active NBT-rTMS. Combining their data with that of the present trial will lead into a trial population of approximately 118 subjects receiving active treatment (88 from NICHE + 30 from the present trial) and approximately 30 subjects receiving sham treatment (all from the present trial). The study power in this population is sufficient to rule out the null hypothesis with 96% power.

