The statistical analysis of the present trial will be performed in two phases. The Bayesian analysis of the E-FIT data combined with data borrowed from the active trial arm of the previously completed NICHE trial (NCT02089464) will be the primary efficacy analysis. Non-Bayesian analysis of the E-FIT trial data only will be performed to demonstrate robustness of the result. Detailed methodology for the analyses is described in a separate statistical analysis plan (Document NX103391 EFIT Statistical Analysis Plan, version 1.0, dated 06 August 2018).

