6.5 SIGNIFICANCE LEVEL

Unless otherwise noted, all statistical analyses will be conducted with a significance level (α) of 0.05 and utilize two-sided testing.

Since the ARAT test has potential to be used for labelling purposes, a Bonferroni adjustment will be employed. A significance level (α) of 0.025 will be used for this secondary analysis only. All other secondary analyses will use $\alpha = 0.05$ as they are not to be used for any labeling purpose.

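### The responder analysis, as written, leaves out baseline Fugl-Meyer score: this may cost some power in the randomised comparison, and it leaves the NICHE-pooled comparison open to confounding by severity

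*Combined protocol and SAP*

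**What the plan says.** - **Endpoint.** A responder gains at least 5 UEFM points between baseline and 6 months after treatment (Protocol Summary). UEFM is measured at the baseline visit (5.2, Visit 2; 5.2.2).
- **Model.** Section 6.0 reports responder proportions "along with the estimated odds ratio, the 95% confidence interval for OR, and the Wald Chi-square test p-value". It names no covariate.
- **Strata and covariates.** Section 6.4: "The primary efficacy analysis will be stratified by length of time after stroke (3-6 months vs. 6-12 months". The additional covariate analyses there use only hours of therapy, which accrue after randomisation.
- **Randomisation.** Section 5.2.3 randomises by site and by time since stroke, not by severity.
- **Primary efficacy analysis.** Section 6.1 gives this role to "The Bayesian analysis of the E-FIT data combined with data borrowed from the active trial arm" of NICHE. It describes 88 NICHE plus about 30 E-FIT active patients against about 30 E-FIT sham patients. The E-FIT-only analysis is there to show robustness. Detailed methods are left to a separate SAP (version 1.0, 06 August 2018), which is not among the documents available for this review.
- **Missing baselines.** Section 6.6.1.2 fills a missing baseline UEFM from the six-month score. If both are missing, it uses the arm's mean baseline.

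**The concern.** The endpoint is a change from a score that is recorded for nearly every patient and then not used in the model. If the chance of a 5-point gain depends on how impaired the arm is at the start, two different things follow.

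In the randomised comparison, adjustment would give a more powerful test at almost no cost, which matters with 30 patients per arm.

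In the pooled comparison the issue is validity. Roughly three quarters of the active group (88/118 = 75%) comes from another trial, while every sham patient comes from E-FIT, so randomisation does not balance severity between these groups. Section 4.2 admits Chedoke-McMaster stages 3 to 6, so two trials with the same eligibility rules can still differ in severity mix. With time since stroke as the only adjustment, such a difference would be read as a treatment effect.

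**Working it through.** **1. The plan's own power figures.** Inputs from 6.1 and 6.5: "sample size calculations utilizing significance level of 0.05 for p", two-sided; "84% of the active NBS-rTMS group and 50% of the sham rTMS group attained clinically significant improvement"; and 72% against an expected 36% from NICHE. The formula is

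power = Φ{(|p1 − p2| − 1.96·s0)/s1}, with s0 = √[p̄(1 − p̄)(1/n1 + 1/n2)] and s1 = √[p1(1 − p1)/n1 + p2(1 − p2)/n2].

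- 84% v 50%, 30 v 30: p̄ = 0.67, s0 = 0.1214, s1 = 0.1132; Φ{(0.34 − 0.2380)/0.1132} = 81.6%.
- 72% v 36%, 30 v 30: p̄ = 0.54, s0 = 0.1287, s1 = 0.1200; Φ{(0.36 − 0.2522)/0.1200} = 81.5%.
- 118 v 30: 96.1% and 95.9%.

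The stated 81% and 96% are therefore unadjusted two-proportion calculations.

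**2. Randomised comparison: gain from adjustment.** The documents give no association between baseline UEFM and response, so a range is assumed: odds ratio 1.65, 2.2 or 3.3 per SD of baseline, linear on the logit. Trials of 30 per arm were simulated (4,000 per cell, simulation error about 0.6 point), with marginal rates held at the plan's values. The Wald test with treatment and stratum only was compared with one that adds linear and quadratic baseline.

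| Odds ratio per SD | 84% v 50%: stratum only → with baseline | 72% v 36%: stratum only → with baseline |
|---|---|---|
| 1.65 | 82.2 → 82.9% | 82.2 → 83.3% |
| 2.2 | 81.5 → 84.9% | 81.7 → 85.0% |
| 3.3 | 81.6 → 87.9% | 82.7 → 88.4% |

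At 3.3, against a Wald test without the stratum, the rise was from 79–80% to 88% and from 82% to 89%, hence a range of about 6 to 8 points. If baseline is not prognostic, adjustment loses at most about 2 points. Type I error of the larger model was 4.7 to 5.7%.

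**3. Pooled comparison: bias from a severity shift.** Suppose E-FIT patients start d SD less favourably than the 88 NICHE patients, whose rate is 72%, and all 88 are pooled at full weight. Then

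bias = (72% − rate after the shift) × 88/118.

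| Odds ratio per SD | d = 0.3 SD | d = 0.5 SD |
|---|---|---|
| 1.65 | (72 − 69.0) × 0.746 = 2.2 points | (72 − 67.0) × 0.746 = 3.8 points |
| 2.2 | (72 − 67.6) × 0.746 = 3.3 points | (72 − 64.4) × 0.746 = 5.7 points |
| 3.3 | (72 − 65.9) × 0.746 = 4.5 points | (72 − 61.6) × 0.746 = 7.8 points |

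A shift the other way reverses the sign. If the relation is instead an inverted U (assumed −0.5 on the logit per squared SD, centred on the NICHE mean), the bias is about 0.7 points at 0.3 SD and just under 2 points at 0.5 SD.

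**4. Pooled comparison: false positives.** 118 v 30 patients, no treatment effect, sham rate 36 to 65%, odds ratio 1.5 to 3 per SD, NICHE patients starting more favourably. The chance of falsely favouring active (nominal 2.5%) was 1.9–2.7% with no shift, 2.8–5.1% at 0.2 SD, 3.1–7.0% at 0.3 SD and 4.7–12.5% at 0.5 SD. With baseline in the model it stayed at 2.0–2.8%.

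**The case against.** The strongest reply is that the pooled half of the point concerns a model nobody can read here. Section 6.1 sends the Bayesian methodology to a separate SAP, which may already include covariates or discount NICHE when it differs. This stands: the absence of baseline UEFM is established for 6.0 and 6.4, not for the Bayesian model.

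The size also rests on assumptions. The only hint that severity is prognostic is the title of a study in the reference list, with no effect size. The bias figures need full-weight pooling and a monotone effect. That stands too, and the ranges should be read accordingly.

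A reader might infer that the pooled result *is* confounded by severity. The documents do not show that. They describe the NICHE population as the same apart from stroke type, restrict borrowing to ischemic patients, claim the same sites and treatment, and give no baseline UEFM for either trial. A difference is possible, not demonstrated.

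A reader might also infer that the randomised E-FIT test is biased or invalid. It is not: omitting a baseline covariate there affects power only.

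Finally, it is tempting to say that every patient has a baseline score. Section 6.6.1.2 plans for patients who do not.

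**Conclusion.** The point holds as a question of efficiency in one comparison and of protection in the other. In the supplied text the responder analysis is stratified by time since stroke alone.

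For the E-FIT-only test, the likely cost is a few points of power, and nothing if baseline is not prognostic. For the NICHE-pooled comparison, the text provides no safeguard against a severity difference. If one exists, the error could be anything from under 1 to about 8 percentage points within the range examined, in either direction, and less if borrowing is discounted. All of this depends on an assumed prognostic strength and an assumed shift. The behaviour of the actual Bayesian model cannot be computed from these documents.

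**What to change.** Before unblinding:

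1. In 6.0 and 6.4, define both the E-FIT-only model and the borrowing model to include treatment, the time-since-stroke stratum and continuous baseline UEFM, allowing for non-linearity (for example a quadratic term, since very low and very high starts may both limit gain).
2. Report the adjusted odds ratio and a standardised risk difference. Keep the raw proportions as description.
3. Tabulate baseline UEFM by trial and arm, so that the comparability of NICHE and E-FIT can be judged.
4. Replace the rules in 6.6.1.2 that fill a missing baseline from the six-month score or the arm mean. Otherwise a post-randomisation value would enter the model as a baseline covariate.
5. If the separate SAP already names covariates for the Bayesian model, reconcile it with 6.4.

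The cost is wording, a revised missing-baseline rule, and one or two degrees of freedom out of 60 patients. No new E-FIT assessment is needed. The NICHE baselines must exist, because its responders could not be classified without them. The adjustment deals with measured severity only. It does not correct drift between the trials or the lack of concurrent randomisation for the 88 borrowed patients.

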8.0 REFERENCES (ALPHABETICAL ORDER)	
APPENDIX A NBT PROCEDURES	
General	
ELECTROMYOGRAPHY	38
MRI TO HEAD CO-REGISTRATION	38
BASELINE, TREATMENT VISITS	
HEALTHY HEMISPHERE	
HAND AREA MOTOR MAPPING	
Attach mapping coil (Nexstim Focal Coil)	39
Identifying the rough location of hand motor area	39
Initial motor threshold measurement for defining intensity for motor map	pping: 40
Mapping of hand motor area and localization of m.EDC hotspot	
THERAPY DELIVERY	41
Attach the TMS coil appropriate for the subject's randomization group	
(Nexstim Trial Coil)	
Motor threshold measurement for defining intensity for rTMS therapy	42
RTMS stimulation	
OFF-LINE ANALYSIS	
APPENDIX B TASK ORIENTED UPPER LIMB THERAPY PROTOCOL	43

PROTOCOL SUMMARY

Title:	E-FIT TRIAL: ELECTRIC FIELD NAVIGATED 1HZ RTMS FOR POST-STROKE MOTOR RECOVERY TRIAL. A PROSPECTIVE, MULTI-CENTER, RANDOMIZED, SHAM- CONTROLLED TRIAL TO DETERMINE THE THERAPEUTIC EFFECTS OF NAVIGATION GUIDED 1 HZ RTMS ADMINISTERED TO THE CONTRALESIONAL HEMISPHERE AS ADJUVANT TO TASK- ORIENTED REHABILITATION IN PATIENTS WITH ISCHEMIC STROKE
Design:	Prospective, double-blinded, randomized, sham-controlled multi-center trial.
Purpose:	To determine whether navigation guided rTMS targeted to the non-lesioned hemisphere in patients with stroke has a beneficial effect on the results of subsequently performed task-oriented motor rehabilitation of the hand.
Study locations:	 A total of 5 centers in the USA Central site : Brain Innovation Center, AbilityLab, Chicago, IL Other participating centers: Burke Rehabilitation Hospital White Plains, New York University of Cincinnati Cincinnati, OH Rancho Los Amigos National Rehabilitation Center Downey, CA Spaulding Rehabilitation Hospital Boston, MA
Principal Investigator:	[name] Medical Director, Center for Stroke Rehabilitation, The Rehabilitation Institute of Chicago, Northwestern University Feinberg School of Medicine.
Enrollment:	60 patients with sub-acute ischemic stroke
Study duration:	18 months
Subject Population:	Patients with subacute stroke (3-12 months after the insult) aged 18 and over with no other brain abnormalities.

PrimaryDetermination of whether 1Hz NBS guided rTMS targeting the motor
representation areas of hand muscles on the non-lesioned brain hemisphere
has a beneficial effect on the motor recovery of the corresponding stroke-
affected muscles when combined with standardized task-oriented motor
rehabilitation.

Primary outcome measure: Upper-extremity Fugl-Meyer score.

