5.2.3 Randomization

Randomization will occur using a random number generator programmed to randomize patients to rTMS vs Sham TMS in a 1:1 ratio such that approximately 30 patients will be randomized to treatment and 30 patients randomized to sham. Randomization will be done separately for each participating site so that the 1:1 ratio for treatment arms will be attained at each participating site. In addition, for each site the randomization will be performed in randomly occurring blocks of 3 to 6 patients. Further, patients who have suffered a stroke 3 to 6 months before the trial will be randomized separately from those who have suffered stroke more than 6 months (maximum 12 months) earlier.

The groups differ only as to the rTMS protocol they receive during the study. The groups are : sham rTMS (900 pulses at 1Hz frequency), and active NBS-rTMS (900 pulses at 110% of motor threshold, 1Hz frequency).

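### Site is a randomisation factor but no planned analysis includes it; if sites differ materially in response, the E-FIT-only test is conservative and loses a little power

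*Combined protocol and SAP*

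**What the plan says.** **Design.** Section 5.2.3 makes site a randomisation factor: "Randomization will be done separately for each participating site so that the 1:1 ratio for treatment arms will be attained at each participating site". It makes time since stroke a second one: "patients who have suffered a stroke 3 to 6 months before the trial will be randomized separately" from those with an older stroke. On blocks it says that "randomization will be performed in randomly occurring blocks of 3 to 6 patients". The protocol summary lists "A total of 5 centers in the USA", and section 5.2.3 plans that "approximately 30 patients will be randomized to treatment and 30 patients randomized to sham".

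**Analysis.** Section 6.4 names time since stroke alone as a stratum: "The primary efficacy analysis will be stratified by length of time after stroke (3-6 months vs. 6-12 months". Its additional covariate analyses add hours of therapy, not site. Section 6.0 reports responder proportions, the odds ratio, "the 95% confidence interval for OR, and the Wald Chi-square test p-value", and names no stratum. The ANOVA that 6.0 gives for the point changes names no site term. No section puts site into an analysis or gives a reason for leaving it out.

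**Which analysis is primary.** Section 6.1 makes a Bayesian analysis that borrows the NICHE active arm the primary efficacy analysis. It describes the non-Bayesian analysis of E-FIT data alone as a check of robustness, and refers to a separate statistical analysis plan for the methods of both.

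**The concern.** Balancing the arms within a factor that predicts outcome reduces the true sampling variation of the treatment comparison. An analysis that omits the factor does not credit that reduction. Its standard error is then larger than the real variation, its interval is too wide, and its test rejects less often than the nominal 5% under the null.

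Site is a plausible predictor here. Therapists deliver the rehabilitation and have discretion over activities (Appendix B), and local assessors score the outcome. The stated power for E-FIT alone is 81%, so there is little to give away. There is also a prespecification gap: with site unmentioned, someone could choose between site-adjusted and unadjusted results after seeing the data.

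**Working it through.** **1. Size of the cells.** 5 sites × 2 time strata = 10 randomisation cells; 60 / 10 = 6 patients per cell on average, about 3 per arm.

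**2. The plan's own power (section 6.1).** Unstratified two-proportion formula, two-sided 0.05: power = Φ[(d − 1.96·s0)/s1], with s0 = √[p̄(1−p̄)(1/n1 + 1/n2)] and s1 = √[p1(1−p1)/n1 + p2(1−p2)/n2].
- 84% v 50%, 30 per arm: s0 = 0.1214, s1 = 0.1132; (0.34 − 0.2380)/0.1132 = 0.901; power 81.6%.
- 72% v 36%, 30 per arm: s0 = 0.1287, s1 = 0.1200; (0.36 − 0.2522)/0.1200 = 0.898; power 81.5%.
- 72% v 36%, 118 v 30: s0 = 0.0977, s1 = 0.0969; (0.36 − 0.1915)/0.0969 = 1.739; power 95.9%.

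The stated 81% and 96% are reproduced. They assume no stratification, so the choice of strata does not make them wrong.

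**3. Error rate and standard error without site.** The documents give no site or time effect, so both were varied. Each simulated trial had 60 patients in 10 cells with permuted blocks of 4 or 6 within cells and a 50% responder rate in both arms; 6,000 trials were run per setting (Monte Carlo error about 0.3 points). CMH is the Cochran-Mantel-Haenszel test. The last two columns refer to the time-only log odds ratio.

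| Site SD (log-odds) | Time log-OR | Type I, time-only CMH | Type I, site × time CMH | Mean model SE | True SD |
|---|---|---|---|---|---|
| 0 | 0 | 5.2% | 5.2% | 0.528 | 0.540 |
| 0.5 | 0.5 | 4.6% | 4.9% | 0.532 | 0.537 |
| 1.0 | 0.5 | 3.5% | 5.2% | 0.531 | 0.500 |
| 1.5 | 1.0 | 2.5% | 5.4% | 0.536 | 0.470 |

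The model SE is about right for absent or modest site effects. It is too large by 0.531/0.500 = 1.06 (6%) at SD 1.0 and by 0.536/0.470 = 1.14 (14%) at SD 1.5. Blocks of 3 to 6 give the same pattern. Across all the simulations, time-only type I error at SD 1.0 lies at about 3.3% to 4.0%.

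**4. Power at 72% v 36%.** Set A uses blocks of 4 or 6 (4,000 trials per setting, Monte Carlo error about 0.6 points). Set B uses blocks of 3 to 6 with random cell sizes, which is closer to section 5.2.3.

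| Site SD | Set | Time-only CMH | Site × time CMH | Logistic, main effects (Wald) |
|---|---|---|---|---|
| 0 | A | 82.4% | 80.2% | not run |
| 0 | B | 81.3% | 78.8% | 81.5% |
| 0.5 | A | 82.7% | 82.0% | not run |
| 0.5 | B | 82.5% | 82.0% | 84.1% |
| 1.0 | A | 83.1% | 86.0% | not run |
| 1.0 | B | 83.4% | 85.6% | 86.2% |

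- At SD 1.0, omitting site costs 86.0 − 83.1 = 2.9 points (A) or 85.6 − 83.4 = 2.2 points (B) against site × time CMH, and 86.2 − 83.4 = 2.8 points against logistic regression.
- At SD 0, full site × time CMH itself costs 82.4 − 80.2 = 2.2 (A) or 81.3 − 78.8 = 2.5 points (B). A further run with blocks of 3 to 6 gave losses of 2.8 and 2.9 points (80.7% v 77.9% with equal recruitment probabilities across sites, 82.4% v 79.5% with unequal). With an idealised 3 + 3 in every cell the loss is only 0.4 points (81.3% v 80.9%), but the blocks in 5.2.3 do not guarantee that balance.
- Logistic regression with main effects does not lose power at SD 0. Its Wald type I error was 5.2% to 5.6% in set B, and up to 6.7% in another run, so part of its apparent gain reflects a slightly liberal test.

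**The case against.** The strongest reply is that these figures do not concern the declared primary analysis. That analysis is Bayesian, its uncertainty depends largely on how 88 borrowed patients who were not randomised in E-FIT are weighted, and site may be handled in the separate plan. This stands: a 30 v 30 simulation bears only on the E-FIT-only robustness analysis. It does not remove the gap, because 6.4 speaks of the primary efficacy analysis and names time since stroke alone.

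Second, a site SD of 1.0 is large. Starting from a 50% site, one SD either way spans about 27% to 73%. The central training and six-monthly re-certification of assessors in section 7.0, and the common therapy protocol in Appendix B, are meant to limit such variation. This also stands, and it makes the size of the loss conditional.

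Third, cells of about six patients are sparse. That is a good argument against the full ten-cell CMH, but not against a model with main effects.

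A reader might infer three stronger things that the documents do not support:
- That the omission threatens validity. The error runs in the conservative direction.
- That the stated power is wrong. It is reproduced on its own inputs.
- That 6.0 and 6.4 contradict each other. Section 6.0 can be read as giving the effect measure and test, with 6.4 adding the stratum.

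**Conclusion.** The mismatch is in the text: two randomisation factors, one of them carried into the analysis and the other not mentioned. Its consequence is conditional and mild. For the E-FIT-only odds ratio, an assumed site SD of 1.0 lowers type I error to about 3.3% to 4.0%, widens the standard error by about 6%, and costs about 2 to 3 points of power. At SD 0.5 or below the effect is negligible. These sizes rest on the assumed site SD, on 60 patients spread over ten cells, and on responder rates of 72% v 36%.

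It would go too far to say that the primary analysis has error bars that do not match the design. That cannot be established without the separate plan, and for the E-FIT-only analysis it is true only to the extent that site predicts response. This is a matter of precision and prespecification, worth correcting because the correction is cheap.

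**What to change.** - In 6.0 and 6.4, state that the E-FIT-only comparison adjusts for both randomisation factors, preferably by logistic regression with main effects for site and time since stroke. Add a rule, fixed before unblinding, for pooling very small sites. Do not make site × time CMH over ten cells the default.
- Use the same two factors for the secondary endpoints.
- Include E-FIT site and time since stroke in the Bayesian primary model, or cross-refer to the separate plan if it already does so.
- Say that the adjusted odds ratio is conditional on site and time, and keep the crude responder proportions alongside it. It will generally lie further from 1 than the ratio defined in 6.0 from the two proportions, and its interval on the log scale need not be shorter.

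If the sponsor prefers to omit site, one sentence justifying that as a deliberate conservative choice would also close the gap.

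The cost is wording and slightly more model complexity. The one statistical price is a Wald type I error of about 5% to 6% in a sample of 60 (6.7% at the highest in one run). The sample size and the stated power need no change.
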